4.4 What is the antileukemic T-cell activity in patients who develop GVHD? All

patients will be regularly monitored for disease status by our standard clinical management techniques, which include (i) morphologic analysis of bone marrow samples to assess "conventional" remission status and (ii) minimal residual disease analyses of marrow and peripheral blood samples using chromosomal markers. As an additional measure of disease recurrence, recipients will be regularly monitored for (iii) the level of donor chimerism in myeloid and lymphoid cells in the blood and marrow, as per our standard institutional protocols. Hence, in patients with myeloid and lymphoid malignancies, we will measure the precursor frequency of CTL specific for the leukemia-associated antigens PR3, PRAME and WT-1 using (i) A2-restricted tetramer assays, (ii) ELISPOT and/or intracellular cytokine assays using pepmix-pulsed PBMC.20

4.5. Do patients with GVHD have impaired NK cell persistence and function? To evaluate NK cell persistence and function post-HSCT, we propose to undertake immunophenotypic analyses of clinical samples obtained post-HSCT. NK-cell persistence will be defined as an absolute circulating NK cell count of >100 cells/µL after HSCT. To address the issue of possible dysfunction of NK cells in patients with GVHD, we propose to perform immunophenotypic analyses of clinical PBMC samples at the timepoints indicated above. Multiparameter (12-color) flow cytometry will be performed for NK cell receptors to evaluate the expression of activating and inhibitory receptors, NK activation and maturation, exhaustion (e.g. CD57 and T-bet)21·22 and homing (e.g. CD62L, CCR7, CLA). Effector function will be assessed by the ⁵¹chromium release assay, CD107a degranulation23·24 and cytokine release (by intracellular cytokine assay [IFNγ]), using K562 and primary leukemia cells collected and stored from recipients pre-transplant. Plasma samples obtained from the recipient before and after HSCT will be assayed for cytokine levels using the BD Cytometric Bead Array for Th1/Th2 cytokines and ELISA assays.

4.6. Statistical analysis. The change in general immune reconstitution in patients with versus without GVHD will be summarized with descriptive statistics. After logarithmic transformation, if deemed appropriate, we will analyze the difference in changes by a two-sample t-test. In addition to descriptive statistics, Treg and antigen-specific T-cell immune reconstitution over time, as measured by phenotyping assays and functional assays will be plotted over time and represented as means ± SD.

4.7. Expected outcomes/potential problems. GVHD is known to be immune suppressive and we predict that there will be an increased Treg response in patients without GVHD with preservation of their cell mediated immune response. Given recent reports in the literature and our own preliminary data, we predict that if there is an increase in Tregs in patients without GVHD, that this will not dampen T-cell immune reconstitution against viral or

leukemia antigens. We also expect the immune reconstitution of NK cells to be unaffected in patients who do not have GVHD but that NK cells in patients with GVHD are either decreased and/or dysfunctional. Although unlikely, we cannot exclude the possibility that NK cells will not be detected in the periphery. This could reflect a complete loss of the NK cells or perhaps their limited expansion in vivo. It is also possible that T-cells and NK cells will home to sites of leukemia, prompting us to look for their presence in the bone marrow as well as blood. We do not anticipate any major obstacles with the proposed immune reconstitution studies, owing to our expertise at the CNMC in multiparameter flow cytometry and T-cell and NK cell functional immunoassays.24-26 However, it is entirely possible that smaller patients will have too few lymphocytes in their peripheral blood, especially in the early post-HSCT period, to accommodate the proposed testing scheme. If so, we will prioritize our tests, requesting additional samples if necessary. Phenotypic analyses, specifically for biomarker assays and CD4⁺ CD25⁺ FoxP3⁺ Tregs, will be performed first, followed by general phenotyping assays (T-cell subsets, NK cells and B cells), functional Treg assays and frequencies of CMV, then EBV and then adenovirus-specific CTL. In patients with evidence of viral infection, evaluation of the T-cell response specific to the infecting virus will be given priority.

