2.2. Eligibility

- All patients receiving an allogeneic hematopoietic stem cell transplant, cord blood transplant, bone marrow transplant, T cell depleted marrow, donor lymphocyte infusion (DLI), or donor cellular infusion (DCI) can be included.
- Patients (or parent/guardian) must have signed the informed consent document

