3. STUDY ENDPOINTS

3.1. Primary endpoint: The primary objective is to confirm that ST2 alone or the seven-biomarker panel measured at initiation of GVHD therapy predict a) D180 post-therapy non-relapse mortality; b) D28 post-therapy non-response, and c) GVHD grade 1-4 onset.

3.2. Secondary endpoints:

- 1. To demonstrate that ST2 alone or the seven-biomarker panel measured at day 14 or day 21 post-HCT (or a combination of these time points) predict D180 post-HCT non-relapse mortality.
- 2. To demonstrate that ST2 alone or the seven-biomarker panel measured at initiation of GVHD symptoms/therapy diagnose acute GVHD as compared to other complications presenting with similar symptoms (drug rash, CMV, Clostridium enteritis).
- 3. To demonstrate that ST2 alone or the seven-biomarker panel measured at initiation of GVHD symptoms/therapy diagnose the severity of acute GVHD at onset and maximum.

3.3. Clinical and histological correlatives:

• Pre-transplant characteristics

Age at transplant, gender, race and ethnicity, Disease diagnosis, disease risk (CIBMTR classification), intensity of conditioning, conditioning regimen, donor source,

HLA-match, stem cell source, other significant pre-HCT diagnoses and clinical characteristics

- GVHD prophylaxis
- Infectious prophylaxis, if any
- Onset Acute GVHD: day of onset, skin stage, liver stage, gastrointestinal stage and overall grade.
- Maximum Acute GVHD: day max, skin stage, liver stage, gastrointestinal stage and max overall grade.
- Biopsies:
 - - yes No,
 - o location skin, upper GI, lower GI, liver
 - GVHD yes or no, other diagnostic, specify
 - This will help identify the incidence of other complications presenting with GVHD symptom that is not GVHD (e.g. infectious diarrhea, drug rash...)
- Systemic therapy
 - Start day
 - Steroids 2 mg/kg/day Yes No
 - Other first line
- Proportion of complete response (CR), Partial response (PR), mixed response, No response, and progression at day 28 post-therapy (among surviving patients)
- Incidence of additional therapy of GVHD given at day 28, and day 56 posttherapy (including for GVHD flare).
- Non-relapse mortality (NRM) at day 180 post-therapy for GVHD patients and NRM at day 180 post-HCT for patients without GVHD.
- Overall survival, GVHD-free survival at day 180 and 360 post-therapy for GVHD patients and NRM at day 180 and 360 post-HCT for patients without GVHD.
- Relapse at day 360 post-HCT.
- Incidence of systemic infections related to GVHD treatment.

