2.2 Recovery of cellular immunity after allo-HSCT. Normal immune reconstitution following HSCT extends over many months and even years, rendering the patient highly susceptible to bacterial, viral, and fungal infections as well as leukemia relapse. Viral infections are one of the leading causes of morbidity and mortality among allo-HSCT recipients. Reactivation of latent viruses such as Epstein-Barr Virus (EBV) and cytomegalovirus (CMV), and infection with community viruses such as adenovirus and RSV are frequent and significant causes of morbidity and mortality.16 Virus-specific T-cells are a critical protective element after allogeneic transplantation,17 and the most prolonged delays in virus-specific immune responses are associated with protocols specifying high levels of T-cell depletion and post-transplant immune suppression to prevent GVHD.

Similarly, several groups have looked at the immune reconstitution of tumor-specific T cells and their effect on relapse. Along with viral infection, we and others have shown that relapse is one of the main causes of failure after allogeneic stem cell transplant. T-cells specific for leukemia associated antigens such as the Wilms tumor antigen (WT1) have been shown to contribute to a graft-versus-leukemia (GVL) effect after allogeneic stem-cell transplantation (HSCT) for acute leukemia. Furthermore, loss of these leukemia specific CD8+ T-cell responses has been shown to be associated with relapse.18 *We hypothesize that a balanced regulatory and virus and leukemia specific T cell recovery prevents GVHD without delaying antiviral immune reconstitution.*

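### Appendix G compares immune recovery with and without GVHD without adjustment, so graft type and GVHD prophylaxis can confound the comparison, in a net direction the documents do not fix

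*Protocol*

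**What the plan says.** Appendix G, section 4.6 of the protocol is the whole analysis plan for the cellular aim. It opens with "The change in general immune reconstitution in patients with versus without GVHD will be summarized with descriptive statistics" and continues "After logarithmic transformation, if deemed appropriate, we will analyze the difference in changes by a two-sample t-test". Treg and antigen-specific T-cell recovery are to be described and "will be plotted over time and represented as means ± SD"; no test or model is planned for them. The section names no covariate, stratification or matching, and gives no sample size or power.

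Four other places bear on this:

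- Appendix G, section 2.2 says the longest delays in virus-specific immunity are "associated with protocols specifying high levels of T-cell depletion and post-transplant immune suppression to prevent GVHD".
- Section 2.2 (Eligibility) admits "cord blood transplant, bone marrow transplant, T cell depleted marrow, donor lymphocyte infusion (DLI" and other products, so T-cell depletion can vary within the cohort.
- Section 3.3 records age, conditioning intensity, donor source, GVHD prophylaxis and "HLA-match, stem cell source, other significant pre-HCT diagnoses and clinical characteristics". It has no separate item for T-cell depletion.
- Appendix C adjusts the protein-panel models for conditioning intensity, HLA match, age and onset grade. The SAP adjusts its plasma-biomarker models for race/ethnicity, malignant disease, graft source and acute GVHD prophylaxis. Neither adjustment extends to the Appendix G assays, which the SAP does not mention.

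**The concern.** Patients are not allocated to GVHD. On the protocol's own account, one set of treatment factors is used to lower the risk of GVHD and also goes with slow recovery of virus-specific immunity. A factor that affects both group membership and outcome is a confounder. An unadjusted contrast attributes its effect to GVHD status.

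At stake is the reading of Appendix G's own questions. Section 4.3 asks whether children with GVHD have poorer pathogen-specific recovery. Section 4.7 predicts that higher Tregs in patients without GVHD will not dampen antiviral or antileukaemic recovery. If the no-GVHD group holds more patients with depleted grafts or heavier immune suppression, that group may look worse for reasons unrelated to being free of GVHD. The t-test and the unadjusted plots give no means of separating the two explanations.

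**Working it through.** Section 4.6 states no figure to reproduce. The check is what the unadjusted difference estimates when one binary factor T (a depleted graft) affects both GVHD and recovery.

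**Inputs**

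- Overall GVHD risk G = 0.50, from the power table in Appendix C.
- Share with depleted grafts q, GVHD risk ratio with depletion r, and slowing of recovery with depletion b (in SD of the analysed quantity). None is in the documents. Assumed ranges: q 0.10-0.30, r 0.4-0.8, b 0.5-1.0.
- True deficit due to GVHD d (in SD), also assumed.

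**Formulas**

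- GVHD risk without depletion: u = G / (q·r + 1 − q); with depletion: r·u.
- Depleted share among GVHD patients: q·r·u / G; among no-GVHD patients: q·(1 − r·u) / (1 − G).
- Unadjusted difference (no GVHD minus GVHD) = d − b × (depleted share in no-GVHD − depleted share in GVHD).

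**Results for the bias term**

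| Case | q | r | b | u | Share, GVHD | Share, no GVHD | Shift (SD) |
|---|---|---|---|---|---|---|---|
| Weak | 0.10 | 0.8 | 0.5 | 0.510 | 0.082 | 0.118 | −0.02 |
| Middle | 0.20 | 0.6 | 1.0 | 0.543 | 0.130 | 0.270 | −0.14 |
| Strong | 0.30 | 0.4 | 1.0 | 0.610 | 0.146 | 0.454 | −0.31 |

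Middle case: u = 0.5 / (0.12 + 0.80) = 0.543 and r·u = 0.326. The shares are 0.2 × 0.326 / 0.5 = 0.130 and 0.2 × 0.674 / 0.5 = 0.270. The difference is 0.139, and × 1.0 SD gives 0.139 SD.

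**Does adjustment remove it?** A simulation (2,000 runs per setting, assumed N = 200, d = 0.30) used a stronger imbalance: q = 0.30, with GVHD risk 0.20 with depletion and 0.63 without. Depleted shares are then 0.12 and 0.48, a difference of 0.36. The unadjusted difference is 0.30 − 0.36b, that is +0.12, −0.06 and −0.24 for b = 0.5, 1.0 and 1.5; the simulation matched these. A linear model with GVHD status and T returned about 0.30 each time.

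**Limits of this arithmetic**

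1. It follows a single confounder. With a second one, the bias becomes −b × (imbalance in T) plus the second factor's effect × its own imbalance. The Pediatric biomarkers part of section 1.3 says younger age goes with less GVHD and names thymic development as a major difference from adults. If younger patients also recover faster, the age term is positive and offsets the first.
2. The plan tests change, whereas the assumed b is most naturally read as a difference in level. Appendix G section 4.1 starts sampling at day +14, and Appendix F takes no PBMCs at day −7 or day 7. If change is counted from day +14, a depleted graft might start lower and rise later, so b for change could be small or of opposite sign.
3. The statement in Appendix G section 2.2 concerns virus-specific responses; the t-test concerns general reconstitution. Applying b to the t-test assumes that the delay extends to general counts.

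**The case against.** The strongest defence is that Appendix G is an exploratory addition. It is absent from the study's listed objectives and endpoints and from the SAP, and it claims no power. Its aim is worded as association, for which an unadjusted comparison is a fair first description. The main biomarker models are already adjusted. This limits the priority of the point but does not remove it: Appendix G states hypotheses, including that balanced recovery prevents GVHD, makes directional predictions and plans a significance test.

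A second defence is that analysing change removes baseline differences, and that samples for the functional assays are frozen only after CD3+ cells reach 500/µL (Appendix G section 4.1), which may partly align patients on recovery. Change scores remove differences in starting level, not factors that drive the rate of recovery. The threshold may weaken the contrast between graft types, but it concerns the functional assays, not the flow-cytometric counts.

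Three stronger readings are tempting, and the documents do not support them:

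- A reader might infer that the bias is known to run against the study's hypotheses, or to reverse a true effect. Only the graft and prophylaxis component has that direction; age may oppose it. Reversal requires b × imbalance to exceed d. Within the table's ranges the largest shift is 0.31 SD, and the clear reversals above use a risk ratio of 0.20 / 0.63 = 0.32, outside those ranges.
- A reader might attach a type I error to the t-test. A shift of 0.139 SD gives z = 0.139 / (2/√n): 0.91 at n = 170 and 1.42 at n = 415, hence rejection rates of about 15% and 29%. But those are the SAP's counts of children aged 10 or under and of the whole cohort including adults. Neither is an Appendix G sample size.
- A reader might take the t-test to cover virus- and leukaemia-specific recovery. It does not; those outcomes have no planned test.

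**Conclusion.** The point holds as a risk of confounding that the plan leaves unaddressed. Section 4.6 makes an unadjusted comparison of non-randomised groups, although Appendix G's own background names a common cause and the eligibility criteria admit the grafts concerned. The gap covers both the t-test and the unadjusted summaries for Treg and antigen-specific recovery.

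The size is not known. The 0.02 to 0.31 SD range rests on assumed values of q, r and b, on one confounder, and on a delay that carries over to the analysed change. It shows that the bias could be negligible or as large as an effect of interest. It does not estimate the bias, and neither a demonstrated reversal nor a known error rate follows from it. This is an inexpensive improvement to a supporting aim; the main biomarker analyses are not affected.

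**What to change.** In Appendix G section 4.6, replace the two-sample t-test with a linear model, or one mixed model over the scheduled days. The outcome should be change on the log scale, or the log value adjusted for the first available value, with the choice stated in advance. Include GVHD status, graft source, GVHD prophylaxis, conditioning intensity, HLA match and age, all listed in section 3.3, and T-cell depletion where it can be derived from the graft and prophylaxis records. Steroids given after GVHD onset lie on the pathway from GVHD to recovery and should not enter as a baseline covariate.

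Report the adjusted difference or geometric-mean ratio with its 95% CI. Apply the same model to the Treg and antigen-specific outcomes, and keep the unadjusted summaries and plots as description.

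The cost is revised wording and a few degrees of freedom, which matter more if few patients yield enough cells. No extra samples are needed. The sponsor must confirm that T-cell depletion is coded, since section 3.3 does not list it; if it is not, it has to be extracted from existing records.

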1. BACKGROUND AND RATIONALE

1.1. Acute Graft-versus-Host Disease (GVHD)

Allogeneic hematopoietic cell transplantation (HCT) is a potential curative therapy for cancers of the blood and bone marrow, including leukemias that represent approximately one third of all cancer cases occurring among children and the leading cause of cancer deaths in children¹. Use of HCT has increased as new techniques have allowed for transplantation in patients who previously would not have been considered HCT candidates. Approximately 30,000 allogeneic HCTs will be performed worldwide in 2020; 20% of allogeneic HCT are performed in the pediatrics population. However, the efficacy of this procedure has been impeded by frequent and severe graft versus host disease (GVHD). The development of GVHD is tightly linked to the beneficial graft versus tumor (GVT) effect, the most potent form of immunotherapy. Nowadays, acute GVHD is measured by clinical symptoms in three organ systems: the skin, liver and gastrointestinal (GI) tract²⁻⁴. Acute GVHD typically occurs between two and eight weeks after transplant, but may occur later⁴, and is often clinically indistinguishable from other causes of clinical symptoms such as conditioning regimen toxicity, infection, or medication. Endoscopic biopsy is often used to confirm the diagnosis^{2,5}, but histologic severity on biopsy has not consistently correlated with clinical outcome^{3,5-7}. A noninvasive, reliable blood biomarker specific for GVHD with strong prognosis information would thus significantly aid in the management of patients with this disorder.

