1. SPECIFIC AIMS

Cellular populations in the peripheral blood may also serve as biomarkers for GVHD (e.g. Tregs). Therefore, we anticipate improving the panel by adding biomarkers of virus and leukemia specific T cell immune reconstitution that will be generated in collaboration with [name]. This integrated proteomic/cellular approach will provide not only candidate biomarkers but also insights in the complex pathology of GVHD.

Accumulating evidence suggests that low levels of circulating Tregs following allo-HSCT in humans are associated with a higher incidence of GVHD in adults, and a causal link between these phenomena is suggested by murine models that show infusion of donor Tregs at the time of transplant or shortly thereafter prevents GVHD while maintaining the graft-versus-leukemia (GVL) effect. We hypothesize that increased donor-derived Tregs detected in the peripheral blood of pediatric patients is associated with a decreased risk of GVHD while sparing the cell mediated immune response to virus and tumor antigens after allo-HSCT. These hypotheses are formulated from extensive preclinical and clinical data and will be tested as follows:

Aim 1: To determine whether increased functional Tregs post allogeneic HSCT is associated with decreased GVHD without affecting cellular immune responses against leukemia and viruses.

We will evaluate patient peripheral blood samples. We will measure recovery of CD4⁺ CD25⁺ FoxP3⁺ T cells as well as other major T-cell subsets using flow cytometry and confirm whether these cells are of donor or recipient origin. We will evaluate the ability of the CD4⁺ CD25⁺ Tregs to suppress alloreactive responses and analyze the mechanism should such suppression occur. We will also measure T-cell immune reconstitution to leukemia antigens (WT1, PR1, PRAME) and viruses (EBV, CMV and Adenovirus) after allo-HSCT. We will measure the frequency of virus and leukemia reactive T cells and test their functionality in cytokine secretion assays.

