2. BACKGROUND AND SIGNIFICANCE

2.1 Regulatory T cells. A subpopulation of T cells that are CD4⁺ CD25⁺ plays a crucial regulatory role in the immune system. These Tregs control autoimmune processes1 and modulate post-transplant alloreactive responses. Tregs constitutively express the transcription factor FoxP3, which is a key regulator of Treg development in humans and mice.2-4 Intracellular expression of FoxP3 is one of the most specific markers for Tregs,5 although other markers such as CD4, CD25^{hi} and CD127^{lo}, may also define the most potent subpopulations.6 In short-term *in vitro* assays, Tregs suppress proliferation of both CD4⁺

and CD8⁺ T cells after polyclonal or antigenic stimulation in a cell contact-dependent and cytokine-independent manner.7 Moreover, interleukin 2 (IL-2) is essential for the generation of Tregs and crucial in maintaining their suppressive function.8 Murine models show that high numbers of Tregs infused at the time of allo-HSCT can prevent GVHD while preserving the GVL effect.9;10⁻11 Indeed, if Tregs present in the transplant product are depleted prior to infusion into irradiated allogeneic recipient mice, GVHD is significantly accelerated.7 Additional studies have shown that Tregs infused post-transplant were able to control established GVHD.4

Human studies have demonstrated that poor Treg reconstitution post HSCT correlate with occurrence of acute or chronic GVHD.12·13 Phenotypic and PCR analyses of FoxP3⁺ regulatory T cells in 57 transplant recipients (27 with active, chronic GVHD and 30 without active, chronic GvHD) showed a decreased frequency of Tregs in patients with chronic GVHD compared to patients without (p<0.0001), and FoxP3 expression was reduced in chronic GVHD patients compared to those without or to controls (p=0.009 and 0.01, respectively).14 Furthermore, there is an association between high donor levels of FoxP3⁺ Tregs and a reduced risk of GVHD after HLA-matched allo-HSCT.15 The above data support efforts to determine in the pediatric setting whether rapid Treg immune reconstitution after allo-HSCT will prevent GVHD.

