4. RESEARCH PLAN

4.1. Immune reconstitution of T-cells and NK cells Blood will be obtained at the designated timepoints (Day +14, +21, +28, +56, +100, +180 and +360 post HSCT as well

as at time of complications such as acute and chronic GVHD onset, start of systemic steroids, or other complications). Peripheral Blood Mononuclear Cells (PBMC) will be obtained by Ficoll separation. Flow cytometric analyses will be used to quantify T cells (CD3+ CD4+ CD8) and T-cell subsets, including naïve and memory T cells, and NK cells. Once the T cells and NK cells have recovered to a predefined level (\geq 500 CD3⁺ cells/µL), samples will be frozen for batch analysis in the functional assays described below (4.2 to 4.5).

4.2. Are functional Tregs increased in pediatric patients without GVHD? To determine Treg phenotype, we will use the intracellular FoxP3 Treg kit (eBioscience) as well as CD4 and CD25 fluorescent antibodies (**Fig. 1A**). Treg induced suppression will be demonstrated by effects on thymidine uptake and CSFE assays in mixed lymphocyte reactions. Specifically, we will examine the response of T cells to a standard APC (Allogeneic PBMC or K562 cells expressing the high affinity IgG receptor CD64) loaded with OKT3. We will determine the mechanism for the suppression by measuring cytokine secretion (IL-10 and TGF- β). For thymidine uptake assays, PBMC will be separated into CD4⁺ CD25⁺ and CD4⁺ CD25⁻ fractions using fluorescent cell-sorting or magnetic bead separation. The CD4⁺ CD25⁻ fraction (responder cells) will be plated into a round-bottom 96-well plate coated with anti-CD3 (OKT3) or allogeneic PBMC. The CD4⁺ CD25⁺ Treg fraction will be added at a 1:1 ratio and incubated at 37⁰C. On day 3, each well will be pulsed with 1 μ Ci of ³H-thymidine. After 18 hours of additional incubation, plates are harvested and processed for counting.20

4.3. Do pediatric patients with GVHD have decreased pathogen-specific immune reconstitution compared to those without? Ten to 40 mL of blood (depending on the patient's size) will be taken at designated intervals post-HSCT to measure the frequencies of virus-specific T cells as well as NK cells. Absolute lymphocyte counts (ALC) will be measured to determine both absolute and relative frequencies of NK cells and virus-specific T-cells. Functional assays will determine the reconstitution of immunity to pathogens frequently detected in patients after allo-HSCT, including EBV, CMV, Aspergillus and adenoviruses.

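### Appendix G asks whether Treg recovery lowers the risk of GVHD, but section 4.6 compares patients by GVHD status without separating samples taken before onset from those taken after

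*Protocol*

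**What the plan says.** The question is set out in Appendix G, sections 1 and 2. Aim 1 is "To determine whether increased functional Tregs post allogeneic HSCT is associated with decreased GVHD". The hypothesis before it is that more donor-derived Tregs "is associated with a decreased risk of GVHD while sparing the cell mediated immune response". Section 2.1 says the evidence supports finding out "whether rapid Treg immune reconstitution after allo-HSCT will prevent GVHD" in children.

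The analysis is in Appendix G, section 4.6. "The change in general immune reconstitution in patients with versus without GVHD will be summarized with descriptive statistics", and then, after a log transformation if appropriate, "we will analyze the difference in changes by a two-sample t-test". The next sentence turns to Tregs and antigen-specific T cells, which are to be described and plotted over time as means ± SD. No other inferential test appears in Appendix G.

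On sampling, section 4.1 states: "Blood will be obtained at the designated timepoints (Day +14, +21, +28, +56, +100, +180 and +360 post HSCT". It adds samples at complications, naming GVHD onset and the start of systemic steroids. On timing, protocol section 1.1 states: "Acute GVHD typically occurs between two and eight weeks after transplant". On the effect of the disease itself, section 4.7 of the appendix states: "GVHD is known to be immune suppressive".

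**The concern.** A claim that Tregs lower the risk of GVHD needs Tregs measured before GVHD begins. Section 4.6 groups patients by an outcome that typically occurs during the sampling period. It does not say when GVHD status is fixed, which days define the change, or how samples taken after onset or on steroids are handled.

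Two explanations then predict the same picture. Under the first, poor Treg recovery permits GVHD. Under the second, GVHD and its treatment depress the counts. Section 4.7 supplies the premise for the second explanation in the same sentence that predicts a greater Treg response in patients without GVHD. A difference between the groups would fit both, and the planned comparison contains nothing to tell them apart. At stake is whether Appendix G can support its own hypothesis, which it presents as a route to adding cellular markers to the GVHD panel.

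**Working it through.** Appendix G gives no sample size, alpha, SD or effect size, so there is no stated figure to reproduce. The check covers time order, the share of samples after onset, and an illustration of size.

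**1. Time order.** Sections 1 and 2 place Tregs before GVHD. Section 4.6 conditions on GVHD and looks at Tregs over days 14 to 360. Time-aware methods do exist elsewhere: Appendix C (Predictive Model) has a Cox model with time-dependent biomarkers, and the SAP uses landmark analyses. Both cover plasma proteins only. The SAP names ST2, IL6, REG3α and TNFR1, and no cellular marker.

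**2. Share of scheduled samples after onset.** Inputs: the seven days in section 4.1, and onset at two to eight weeks (section 1.1), assumed uniform over days 14 to 56. The share of GVHD patients past onset on day d is (d − 14)/42, held between 0 and 1.

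- Day 14: 0
- Day 21: 7/42 = 0.167
- Day 28: 14/42 = 0.333
- Days 56, 100, 180 and 360: 1 each

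The sum is 0.167 + 0.333 + 4 = 4.5, and 4.5/7 = 64%.

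**3. Chance of a significant difference with no pre-onset difference.** All inputs are assumed: 100 patients per group, SD of log change s = 0.7, a two-sided 5% test, and 60% of the GVHD group with a later sample after onset. The 60% lies between the day 28 (33%) and day 56 (100%) shares above. Post-onset counts fall by a fraction r.

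- Mean difference: 0.6 × ln(1 − r)
- Variance in the GVHD group: s² + 0.6 × 0.4 × [ln(1 − r)]²
- Standard error: √[(s² + variance in the GVHD group)/100]

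| r | Mean difference | Standard error | Ratio | Chance of p < 0.05 |
|---|---|---|---|---|
| 20% | −0.134 | 0.0996 | 1.34 | 27% |
| 35% | −0.259 | 0.101 | 2.55 | 72% |
| 50% | −0.416 | 0.105 | 3.97 | 98% |

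Simulation agrees: 27%, 72% and 97–98%, and 5% when r = 0. For s from 0.6 to 0.9 the range is about 18–35% at r = 20% and 87–99% at r = 50%.

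**4. Dependence on which change is tested.** A second simulation used a 50% GVHD rate (the figure in the Appendix C power table), uniform onset, SD of change 1, and a post-onset shift of 0.3 or 0.5 SD. Total N and the shift are assumed.

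| N | Day 100 − day 14, 0.3 SD | Same, 0.5 SD | Day 28 − day 14, 0.3 SD | Same, 0.5 SD |
|---|---|---|---|---|
| 60 | 22% | 48% | 7% | 9% |
| 100 | 30% | 70% | 7% | 13% |
| 170 | 50% | 91% | 10% | 19% |
| 350 | 80% | >99% | 16% | 32% |

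When only patients still GVHD-free at day 21 or day 28 were compared, on samples up to that day, the rate was 4.3–5.6% for every N and for every shift from 0 to 0.8 SD.

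**The case against.** The strongest reply is about what section 4.6 actually tests. The t-test sentence names general immune reconstitution, and Tregs come only in the descriptive sentence after it. A reader might infer that the plan t-tests Tregs between the groups. The text does not say so. This stands: Aim 1 has either that t-test or no named test. It does not remove the timing problem, because Treg means plotted by GVHD status mix pre-onset and post-onset samples in the same way.

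Second, Aim 1 speaks of association, section 4.2 asks a plain group question, and the prediction in section 4.7 comes with the remark that GVHD suppresses immunity. The authors may not intend a causal reading. That is fair for the wording of the aim. The hypothesis in section 1, however, is stated as risk, and section 2 speaks of prevention.

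Third, a reader might take the percentages as an inflated type I error of the t-test. They are not. In these scenarios the group means really differ, and the test is right to say so. The error would lie in attributing the difference to Treg protection.

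Fourth, sections 4.3 and 4.5 ask whether GVHD patients have impaired pathogen-specific and NK-cell immunity. Comparison by GVHD status suits those questions, so the criticism does not extend to the whole appendix.

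Finally, Treg analysis is in neither the primary nor the secondary objectives, nor in the SAP. That limits the consequence to Appendix G. It does not make the comparison answer the question posed there.

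**Conclusion.** The point holds for Aim 1 and section 4.2 of Appendix G. The planned comparison by GVHD status cannot separate Treg protection from the effect of GVHD and its treatment, and nothing elsewhere in the protocol or SAP repairs this for Tregs.

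The 64% rests on uniform onset over weeks 2 to 8. The chances of 27%, 72% and 97–98% rest on an assumed sample size, SD, post-onset share and reduction. They show how easily a difference open to misattribution could arise, and they are not predictions for this study. The exposure is much smaller if the change is measured only to day 28 (7–16% at a 0.3 SD shift, against 22–80% for day 100). The protocol does not say which change is meant. This should be corrected, but it does not touch the study's primary or secondary endpoints.

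**What to change.** Amend Appendix G section 4.6 for Aim 1 and section 4.2 only:

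- Test the Treg–GVHD association on samples drawn before GVHD onset and before systemic steroids for GVHD.
- Take time to acute GVHD as the outcome, with the latest pre-onset Treg count as a time-updated covariate. Alternatively, use a day 21 or day 28 landmark in patients still GVHD-free.
- Treat death and relapse as competing events.
- Report post-onset and on-steroid Treg data descriptively, labelled as possibly caused by GVHD and its treatment.
- Keep the comparison by GVHD status for sections 4.3 and 4.5, and state which days define the change.

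The dates and samples are already planned. Protocol section 3.3 records the day of GVHD onset and the start of systemic therapy, and Appendix F banks mononuclear cells at days 14, 21 and 28.

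The cost is information. Early-onset patients contribute few samples or none, since the first cell sample is at day 14. Section 4.7 warns that small patients may have too few lymphocytes early on, although it puts Treg phenotyping first when cells are scarce. Section 4.1 also holds the section 4.2 assays until a CD3+ threshold is reached. The amended text should therefore say whether early Treg phenotyping depends on that threshold, because the pre-onset analysis needs those counts.
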